Study Design and Methodology:	This will be a nonrandomized, open-label, pilot, observational, phase IV study to evaluate the compliance with and perceptions of treatment, as w as HRQOL in surgically resected melanoma patients undergoing HDI or PEG IFN therapy. The study will consist of a pretreatment (screening) phase, an induction phase, a maintenance phase, and an end-of-study (EG assessment.  Pretreatment/Screening							
	All patients will undergo a standard medical screening within 28 days of study of the first administration of HDI or PEG IFN.							
	Induction Phase							

	All enrolled patients will be offered HDI or PEG IFN and, after discussion with their treating physician, will initiate the therapy of their choice. Suggested dosing per package insert is as follows, but can be altered per institutional guidelines.					
	HDI: 20 million IU/m  as an intravenous (IV) infusion over 20 minutes, 5 consecutive days per week for 4 weeks					
	or PEG IFN: 6 mcg/kg/week subcutaneously (SC) for 8 doses					
	Patients will complete the CCSQ and evaluate the treatment-related side effects that may impact their HRQOL using the FACT-BRM at specified time points during the Induction Phase.  Maintenance Phase					
	During the Maintenance Phase, patients will receive:					
	HDI: 10 million IU/m  as an SC injection 3 times per week for 48 weeks					
	or PEG IFN: 3 mcg/kg/week SC for up to 5 years (only the first year of therapy will be evaluated in this study)					
	This is again the suggested dosing per package insert, and can be altered per institutional guidelines.					
	As in the Induction Phase, patients will complete the CCSQ and FACT-BRM evaluations at specified time points.					
	End-of-Study Assessment					
	All patients who receive HDI or PEG IFN will be requested to return for an EOS visit within 21 days of discontinuation of study treatment. Final diary collection, safety assessments, treatment perceptions and HRQOL evaluations will be conducted at this visit.					
	Safety assessments will be conducted during the study via clinical laboratory tests and adverse event (AE) monitoring.					
Inclusion Criteria:	To be eligible for enrollment in this study, each of the following criteria must be satisfied with a "YES" answer (unless not applicable):					
	1. Patient is a male or female at least 18 years of age					
	2. Patient has had surgically resected melanoma and plans to receive					

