#### **Toxicity and Quality of Life on Interferon Therapy**

The use of adjuvant HDI is associated with considerable toxicity, most prominently flu-like symptoms and depression, resulting in a high rate of discontinuation. Despite this, over 60% of patients are able to complete 1 year of therapy. Treatment with PEG IFN produces similar side effects to those seen in patients treated with HDI, but at a lower intensity (Loquai 2008).

The value of HDI adjuvant therapy, with its attendant side effects, is an area of interest for prescribing physicians. Investigators question whether patients view HDI treatment positively because there is only a modest benefit in RFS without an improvement in OS. In 2002, a study was conducted to evaluate quality of life (QoL) of high-risk melanoma patients who received HDI versus observation for patients enrolled on 2 cooperative group trials (E1684 and E1690/S9111/C9190) (Kilbridge 2002). The study analyzed the trial efficacy, utility data, and quality-adjusted time without symptoms or toxicity to estimate the effect of HDI on QoLadjusted survival (QAS). When the study evaluated patients enrolled in the E1684 study, a significant increase in QAS was found for all patient subsets but the result was statistically significant for only 16% of patients. For patients enrolled in the E1690/S9111/C9190 trial, QAS improvement was seen for 77% and a decrease was seen for 23%. Neither of the groups was statistically significant. In both trials, the change in QAS depended more on the utility for HDI toxicity than on the utility for melanoma recurrence.

A study has also been conducted to evaluate the effect of PEG IFN therapy on QoL. This study performed a retrospective evaluation using the EORTC QLQ-C30 QoL questionnaire. Both patients and physicians were asked to report on the patients' physical condition, mental health, and social life at baseline and throughout the course of treatment. The dose of PEG IFN given was lower than the current standard, at 2 mcg/kg per week for 18 months. For all functional domains analyzed, patients reported a decrease from baseline in their ability to function while on PEG IFN treatment. Similarly, as expected, there was an increase in constitutional symptoms with fatigue and loss of appetite being the most highly affected. Despite the significant impact of treatment on the QoL, patients still assessed their QoL as good on PEG IFN treatment.

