#### 5.4.1 Treatment Discontinuation and Premature Patient Withdrawal

The investigator may at any time determine that a patient should no longer receive treatment with HDI or PEG IFN for reasons related to patient safety or for other reasons. If a patient's treatment with interferon is permanently discontinued, all study procedures will also be discontinued. All data obtained prior to treatment discontinuation will be included in the analysis set.

Patients may voluntarily withdraw from the study for any reason at any time. They may be considered withdrawn if they state an intention to withdraw, or fail to return for visits, or become lost to follow up for any other reason.

If premature withdrawal occurs for any reason, the investigator must determine the primary reason for a patient's premature withdrawal from the study and record this information on the Study Completion case report form (CRF). Patients who are prematurely withdrawn from the study will not be replaced.

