- g Chemistry labs will be done as clinically indicated and should include albumin, creatinine kinase (CPK), urea or blood urea nitrogen (BUN), creatinine, alanine aminotransferase (ALT), aspartate aminotransferase (AST), lactate dehydrogenase (LDH), serum alkaline phosphatase, direct and total bilirubin, glucose, total protein, sodium, potassium, chloride, bicarbonate (HCO3) (CO2; venous blood), calcium, and phosphorous. Chemistries should be performed weekly during the induction phase or according to institutional protocol. Specific individual chemistry labs may be omitted according to investigator judgment if not included in the institution's chemistry profile.
- h All Grade 3 and 4 adverse events (regardless of whether they occur on treatment or non-treatment weeks) will be collected until the last day of treatment and submitted utilizing the corresponding AE forms. Additionally, all SAEs, regardless of grade will also be collected.
-  Treatment perceptions and HRQOL data will be collected via CCSQ and FACT-BRM, respectively, at baseline, every 2 weeks during the induction phase, and monthly during the maintenance phase (beginning at day 29) for up to 1 year. These questionnaires are to be completed prior to the administration of the dose for that visit. If dose is held or changed QoL is still to be completed.
- j Patients will be instructed to record details on the receipt of HDI in the drug administration diary and will return the diary to the site at the subsequent visit. These diaries will capture the onset of AEs in relationship to the day of drug administration.

Table 3: Schedule of Events (Cohort B: PEG IFN) Suggested schedule of events (QOL evaluation is mandatory)

Test/Assessment	Pretreatment a	D1	D8 b	D15 b	D22 b	b	b	b	Maintenance Phase c
Informed consent	X								
Medical history	X								
Interferon preference questionnaire	X								
ECOG PS	X								
Weight/vital signs d		X	X	X	X				X
Physical examination e		X							X
Hematology labs f		X	X	X	X				X
Chemistry labs g		X	X	X	X				X
Collection and Monitoring of		X	X	X	X				X
Grade 3 and 4 AE and all SAEs h									
QoL evaluations i		X		X					X
Drug administration diary j		X	X	X	X				X

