Item CS13, which rates the chemotherapy regimen overall, will be presented descriptively for the two treatment groups at the end of the study (i.e., 12 months). No inferential analyses will be conducted for this item.

- To evaluate the treatment-related side effects that may impact the patient's health-related QoL (HRQOL) using the Functional Assessment of Cancer Therapy of Biologic Response Modifier (FACT-BRM), with a 30% between-group difference in scores deemed clinically relevant, a mixed randomized-repeated measures ANOVA will be conducted for all items as a summation score, similar to the analysis plan described for CCSQ items CS1 GP5 (page 23, second bullet point). Separate subscales will be presented descriptively for the two treatment groups.
- The frequency of Grade 3 and 4 toxicities, according to the National Cancer Institute (NCI) Common Toxicity Criteria for Adverse Events (CTCAE) for patients on standard HDI versus PEG IFN, will be presented descriptively for the two treatment groups at 2 weeks, 3 months, 6 months and 12 months. No inferential analyses will be conducted for this outcome.
- Patients' reasons for their choice of treatment with HDI versus PEG IFN, for those cases in which patients are presented with a choice of either treatment option, will be reported descriptively at the study's conclusion (i.e., 12 months). No inferential analyses will be conducted for this outcome.

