Data Analysis -REVISED JULY 2023

Due to the study's pilot study design, sample size was not calculated formally. For both primary and secondary outcomes, descriptive data are presented (i.e., medians and ranges for continuous data, frequencies and percentages for categorical data).

Although the original data plan called for exploratory mixed randomized-repeated measures analysis of variance (ANOVA) to be conducted for the primary and two secondary outcomes, the pattern of missing data across patients at the designated time points was too prevalent (and appeared not to be missing at random) to ensure robust ANOVA results. Therefore, we reported separate non-parametric statistical outcomes when deemed feasible (i.e., adequate and balanced subgroup sample sizes) in an attempt to obtain as much information as possible about data trends and patterns. Because we were unable to capture within-subject correlations over time, as well as the treatment group*time interaction, our results should be interpreted accordingly.

The primary outcome was compliance with HDI and PEG IFN (i.e., percentage of doses taken based on total doses required over 53 weeks, as recorded in patient diaries), with a difference of 30% between groups deemed clinically relevant. We reported frequencies and percentages per week and an overall percentage of doses taken at the end of 53 weeks, with statistical analysis of this outcome.

Secondary outcomes were as follows (with different time points reported depending on the highest outcome frequencies):

- Comparison of the convenience and satisfaction with chemotherapy for patients on standard HDI versus PEG IFN using a chemotherapy convenience and satisfaction questionnaire (CCSQ), summation of items CS1 – GP5, with a 30% between-group difference deemed clinically relevant. Time points of comparison were baseline/week 1, week 3, week 13, week 25, and week 50.
- Item GF7, which assesses contentment with current quality of life, at baseline/week 1, week 3, week 13, week 25, and week 49.
- Item CS10, which assesses satisfaction with current results of chemotherapy, at week 1, week 3, week 13, week 25, week 37, and week 45.
- Items CS11 and CS12, which measure recommendation/choice of chemotherapy regimen, at week 1, week 3, week 13, week 25, week 37, and week 45.
- Item CS13, which rates the chemotherapy regimen overall, at week 1, week 3, week 13, week 25, week 37, and week 45.

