- Treatment-related side effects that may impact the patient's health-related QoL (HRQOL) using the Functional Assessment of Cancer Therapy of Biologic Response Modifier (FACT BRM), with a 30% between-group difference in scores deemed clinically relevant. Time points of comparison were baseline/week 1, week 3, week 13, week 25, and week 50.

- The frequency of Grade 3 and 4 adverse events (AEs), according to the National Cancer Institute (NCI) Common Toxicity Criteria for Adverse Events (CTCAE) for patients on standard HDI versus PEG IFN, and the frequency of severe adverse events (SAEs), regardless of grade.
- Patients' reasons for their choice of treatment with HDI versus PEG IFN at the study's conclusion, for those cases in which patients were presented with a choice of either treatment option.

All analyses were conducted using IBM SPSS Statistics for Windows, Version 25.0 (Armonk, NY: IBM Corp.), with $p < .05$ denoting statistical significance.

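### Grade 3/4 AEs and SAEs are compared as unadjusted frequencies although Grade 3/4 collection ends with treatment, which tends to understate toxicity in the arm with shorter exposure

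*SAP*

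**What the plan says.** **Measure.** The SAP's AE item is "The frequency of Grade 3 and 4 adverse events (AEs" for HDI versus PEG IFN, plus SAEs of any grade. Its general rule is "frequencies and percentages for categorical data". The item states no denominator, observation window or time points. Protocol section 3 names the comparison of Grade 3 and 4 AEs between arms as a secondary endpoint. Section 9.2 adds a summary by body system and preferred term, with no exposure adjustment.

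**Time points.** Protocol section 9 says these toxicities "will be presented descriptively for the two treatment groups at 2 weeks, 3 months, 6 months and 12 months", with no inferential analysis. The SAP's AE item drops those times, although its questionnaire items name specific weeks.

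**End of observation.** Footnote h of Tables 2 and 3 says Grade 3/4 AEs "will be collected until the last day of treatment and submitted utilizing the corresponding AE forms"; its sentence on SAEs gives no end date. Section 5.4.1 adds: "If a patient's treatment with interferon is permanently discontinued, all study procedures will also be discontinued". Against this, the synopsis requests an "EOS visit within 21 days of discontinuation of study treatment", with safety assessments, and section 7.1 follows each detected AE until it resolves or is judged permanent.

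**Expected stopping.** The protocol background describes HDI toxicity as "resulting in a high rate of discontinuation", puts one-year HDI completion above 60%, and describes PEG IFN side effects as similar but less intense.

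**The concern.** A patient who stops at month 3 contributes about three months in which a Grade 3/4 AE can be recorded; a patient who completes contributes about twelve. A count or percentage per patient enrolled treats the two alike. If one arm stops earlier on average, part of any difference in AE frequency reflects observation time rather than toxicity. The protocol itself foresees substantial stopping on HDI and links it to toxicity, so unequal exposure is a realistic prospect.

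The study is meant to show whether a larger trial is warranted, and tolerability bears on that decision. Readers will compare the two AE percentages even though they are labelled descriptive. Non-randomised allocation already limits the comparison. Unequal observation time is a second source of distortion, and much of it can be made visible with data already collected.

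**Working it through.** The documents give no AE rate, exposure time or power for this outcome, so there is no planned figure to reproduce. The calculations below are illustrative.

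**Inputs**
- HDI one-year completion: 60% (the protocol background says over 60%).
- PEG IFN one-year completion: not given; assumed 30% to 90%.
- Grade 3/4 event rate h: not given; assumed 0.3 to 1.5 per patient-year, the same in both arms.
- Window: 1 year (protocol section 3). Observation ends with treatment (footnote h).
- Stopping at a constant rate (assumption).

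**Formulas.** With completion c, the stopping rate is l = −ln(c) and mean time on treatment is (1 − c)/l years. Expected events per patient are h × mean time. The probability of at least one recorded event is h/(h + l) × [1 − exp(−(h + l))].

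**Step 1: exposure**
- HDI, c = 0.60: l = 0.511; mean 0.40/0.511 = 0.783 years (9.4 months).
- PEG IFN, c = 0.40: l = 0.916; mean 0.60/0.916 = 0.655 years.
- PEG IFN, c = 0.80: l = 0.223; mean 0.20/0.223 = 0.896 years.

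**Step 2: crude events per patient, equal true rates.** h cancels, so the PEG IFN/HDI ratio is the ratio of mean times.

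| PEG IFN completion | 30% | 40% | 50% | 60% | 70% | 80% | 90% |
|---|---|---|---|---|---|---|---|
| Crude ratio (true ratio 1.00) | 0.74 | 0.84 | 0.92 | 1.00 | 1.07 | 1.15 | 1.21 |

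**Step 3: percentage of patients with an event**

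| h per year | HDI (60%) | PEG IFN (40%) | PEG IFN (80%) |
|---|---|---|---|
| 0.3 | 20.6% | 17.4% | 23.4% |
| 0.7 | 40.6% | 34.7% | 45.7% |
| 1.5 | 64.6% | 56.5% | 71.5% |

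Reporting percentages as well as counts does not remove the effect.

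**Step 4: events concentrated early.** Let the rate be 2.4 per year in the first 8 weeks and 0.6 afterwards, in both arms. Events per patient are 0.736 (HDI), 0.651 (PEG IFN 40%) and 0.810 (PEG IFN 80%). The crude ratios shrink to 0.88 and 1.10.

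**Step 5: stopping driven by toxicity.** Suppose 60% of Grade 3/4 events end treatment and the true rates are 1.5 and 0.5 per year.
- Stopping rates are 0.6 × 1.5 = 0.9 and 0.6 × 0.5 = 0.3, so completion is exp(−0.9) = 41% and exp(−0.3) = 74%.
- Mean times are 0.659 and 0.864 years.
- Crude events per patient are 1.5 × 0.659 = 0.99 and 0.5 × 0.864 = 0.43, a ratio of 2.3 against a true 3.0.

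The more toxic arm stops earlier and still shows more events; its excess is reduced, not reversed. In this model the percentage with at least one event loses nothing, because a stop caused by an event comes after that event has been counted.

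**Step 6: would one overall rate repair this?** With constant rates, yes: the ratio is 1.00 throughout. With the early concentration of step 4, no. Overall rates per patient-year are 0.736/0.783 = 0.940 (HDI), 0.651/0.655 = 0.994 (PEG IFN 40%) and 0.810/0.896 = 0.904 (PEG IFN 80%). The ratios are 1.06 and 0.96 although the true rates are identical in each period. The error now runs against the shorter-exposed arm. Rates by period avoid it.

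**The case against.** The strongest reply is that this is a non-randomised pilot, the protocol rules out inference on AEs, and on-treatment frequency is a legitimate descriptive summary. That stands, and it limits the consequence. It does not justify leaving exposure out of a comparison between arms.

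A reader might infer that the earlier-stopping arm will look safer. The documents do not support that. They tie HDI stopping to toxicity, and step 5 shows that such stopping can merely shrink a true excess. Nor do they show which arm stops earlier, since no PEG IFN completion figure is given.

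A reader might also assume mean exposures of 8 and 11 months with equal hazards and expect a false gap of 9 to 12 percentage points. Under constant-rate stopping, an 8-month mean implies about 42% completion, which fits poorly with the protocol's figure of over 60% on HDI (about 9.4 months at 60%). Equal hazards also cannot illustrate a bias in favour of the more toxic regimen.

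Three further points have weight. The protocol's fixed time points would not have removed the problem, because patients who have stopped are equally unobserved at 6 and 12 months. The SAP plans percentages as well as counts. And observation may not end exactly with treatment, given the end-of-study visit; but that adds at most about 21 days and conflicts with section 5.4.1.

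**Conclusion.** The point holds as a worthwhile, inexpensive improvement. Grade 3/4 AE collection ends with treatment, the arms are to be compared, and neither document plans to show or adjust for time under observation. The resulting frequencies tend to understate toxicity in the arm with shorter exposure.

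Neither the direction nor the size can be derived from the documents. Under equal constant rates and 60% HDI completion, the crude event ratio runs from 0.74 to 1.21 across the assumed PEG IFN completion range. The distortion is smaller if events cluster early. Stopping caused by a Grade 3/4 event affects event counts more than the percentage of patients with an event. A reversed ranking needs similar true rates, or an exposure gap that outweighs the rate gap; it is possible but not demonstrated.

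**What to change.** 1. Keep the planned frequencies and percentages, and state the denominator.
2. Beside them, report the patient-time of AE observation in each arm.
3. Give Grade 3/4 AEs and SAEs per patient-month with 95% CIs by common calendar period from first dose, for example 0–8 weeks, 8 weeks to 6 months and 6–12 months. Do not rely on a single overall rate (step 6).
4. Restore the protocol's AE time points (2 weeks, 3, 6 and 12 months) with the number still under observation in each arm.
5. If cumulative incidence of the first Grade 3/4 AE is added, state how discontinuation is handled and show both versions. Censoring assumes that stopping is non-informative, which is doubtful here. Treating it as a competing event gives on-treatment risk and largely reproduces the crude percentage.
6. Reconcile the synopsis end-of-study visit, section 5.4.1, footnote h of Tables 2 and 3, and section 7.1 on when AE observation ends, including for SAEs, and use that date for patient-time.

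The cost is a small amount of extra analysis. AE start and end dates are on the CRF and dosing is in the diaries, so no new collection is foreseen. Diary dates may be incomplete, so the report should say how many patients lack a usable last-dose date and how they were handled.

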Statistical Methods:	This is an observational pilot study; therefore, descriptive outcomes will be presented comparing primary and secondary endpoints between patients receiving HDI versus PEG IGN. Selected inferential statistical comparisons will be conducted for exploratory purposes only and based on estimated clinically meaningful between-group differences, rather than statistically determined effect sizes					
Date of Protocol:	Protocol Amendment (Version 2.0): 25 March 2014 Original (Version 1.0): 27 June 2013					

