#### • Secondary outcomes:

• To compare the convenience and satisfaction with chemotherapy for patients on standard HDI versus PEG IFN using a chemotherapy convenience and satisfaction questionnaire (CCSQ), with a 30% between-group difference in scores deemed clinically relevant, a mixed randomized-repeated measures ANOVA will be conducted for items CS1 – GP5 as a summation score, since these items share the same Likert scale anchors and valences. Treatment group (HDI versus PEG IFN) will comprise the randomized (betweengroup) factor and treatment period time represents the repeated measures (withingroup) factor. For the repeated measures factor of time, given the different induction phases for the two regimens (i.e., approximately 4 weeks for HDI versus 8 weeks for PEG IFN), the ANOVA will capture outcomes at baseline, 2 weeks, 3 months, 6 months and 12 months, with inclusion of the latter outcome dependent on the amount of missing data.

It should be noted that although the CCSQ is technically an ordinal tool, it will be treated as a continuous/interval scale for the purposes of the ANOVA, with transformation of outcomes as deemed appropriate. It should also be noted that the CCSQ has not been formally validated; therefore, certain items will be presented descriptively, rather than inferentially, as per the judgment of the study authors in keeping with the study's exploratory nature.

Item GF7, which assesses contentment with current quality of life, will be presented descriptively for the two treatment groups as a separate item due to its positively worded valence, at baseline, 2 weeks, 3 months, 6 months and 12 months. No inferential analyses will be conducted for this item.

For item CS10, which assesses satisfaction with current results of chemotherapy, the 3 separate "yes" responses will be collapsed for the sake of convenience and presented descriptively as a dichotomous outcome for the two treatment groups at 2 weeks, 3 months, 6 months and 12 months. No inferential analyses will be conducted for this item.

Items CS11 and CS12, which measure recommendation/choice of chemotherapy regimen, will be presented descriptively for the two treatment groups at 2 weeks, 3 months, 6 months and 12 months. No inferential analyses will be conducted for these items.

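### The SAP applies an unadjusted p<.05 significance rule to all analyses and drops the protocol's exploratory-only limit and its bar on testing single CCSQ items

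*SAP*

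**What the plan says.** **Protocol.** The Synopsis (Statistical Methods) states: "Selected inferential statistical comparisons will be conducted for exploratory purposes only". Section 9 repeats that restriction. Section 9 plans a mixed repeated-measures ANOVA for three outcomes: compliance, the summed CCSQ items CS1 to GP5, and the FACT-BRM total. For GF7 and for CS10 it says: "No inferential analyses will be conducted for this item". Equivalent statements cover CS11 and CS12, CS13, Grade 3 and 4 toxicities, and reasons for treatment choice. CS13 was to be shown at 12 months only.

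**SAP (Data Analysis, revised July 2023).** The ANOVA had been intended "to be conducted for the primary and two secondary outcomes", but missing data were too common and seemed not to be random. In its place, "we reported separate non-parametric statistical outcomes when deemed feasible", with feasibility defined by subgroup sizes that are large enough and balanced. For compliance the SAP reports weekly figures and "an overall percentage of doses taken at the end of 53 weeks, with statistical analysis of this outcome". Secondary time points vary with where most data were available. The CCSQ sum and FACT-BRM each have five time points of comparison. GF7 is listed at five weeks, and CS10, CS11, CS12 and CS13 at six weeks each. The last sentence names the software for all analyses and gives p<.05 as "denoting statistical significance". No multiplicity adjustment appears anywhere.

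**The concern.** A threshold described as denoting significance tells the reader that each flagged result carries a 5% error rate. That does not hold for a set of separate tests at several visits when the number of tests is not stated and the visits were settled after data availability was known. The protocol dealt with this by calling all inference exploratory and by keeping the single items out of testing. The SAP uses the word exploratory only for the abandoned ANOVA and does not repeat the bar on single items.

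The stake is practical. Protocol sections 1.2 and 9.3 say the 100 patients should show whether a larger trial is warranted. One visit with p<.05 on a questionnaire, reported as significant, could be given more weight in that decision than it deserves.

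**Working it through.** Neither document gives a number of tests or a family-wise error rate, so there is no stated figure to reproduce. The check counts comparisons and applies the SAP's threshold.

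**Inputs from the SAP:** threshold 0.05 per comparison (sidedness not stated, taken as two-sided; no adjustment); compliance, 1 overall comparison; CCSQ sum, 5 time points; FACT-BRM, 5; GF7, 5; CS10, 6; CS11 and CS12, 2 × 6 = 12; CS13, 6.

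**Formula.** With k independent tests and no true difference, P(at least one p<.05) = 1 − 0.95^k. The expected number of false positives is 0.05k at any correlation.

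**Comparisons the SAP marks for testing.** Only compliance is given a statistical analysis by name, and only the CCSQ sum and FACT-BRM have time points of comparison. These are also the only three outcomes with the 30% clinically relevant difference.
- k = 1 + 5 + 5 = 11
- 1 − 0.95^11 = 0.431
- Expected false positives: 11 × 0.05 = 0.55

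**Ceiling if every listed outcome and week were tested.**
- k = 1 + 5 + 5 + 6 + 12 + 6 + 5 = 40
- 1 − 0.95^40 = 0.871
- Expected false positives: 40 × 0.05 = 2.0
- Of the 40, 5 + 6 + 12 + 6 = 29 fall on items the protocol bars from testing.

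**Correlation.** Repeated scores on the same patients are correlated, and the documents give no value. Two assumed structures show the range:

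| Assumption | 11 tests | 40 tests |
|---|---|---|
| Independence | 43.1% | 87.1% |
| Time correlation 0.3-0.7, between-outcome 0.2-0.5 (simulated, 200,000 draws) | 28-40% | 59-83% |
| Common correlation 0.5 | 30.4% | 57.1% |
| Common correlation 0.7 | 22.3% | 37.5% |

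**Comparison with the protocol's plan.** A mixed ANOVA gives both a group test and a group-by-time test. Three outcomes therefore already meant 3 × 2 = 6 arm-related tests, and 1 − 0.95^6 = 0.265 if independent. On the reading the SAP best supports, the number rises from about 6 to about 11. The protocol labelled its tests exploratory; the SAP does not label its replacements.

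**The case against.** The strongest reply is that the SAP never says the single items were tested. The separate tests are introduced as the replacement for an ANOVA that covered three outcomes. The GF7 and CS10 to CS13 entries name an item and some weeks but no comparison, and the SAP says descriptive data are presented for all outcomes. Failing to repeat a prohibition does not lift it. This stands, so 40 is a ceiling only.

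The reply can be pressed further. Two of the 11 comparisons are at baseline/week 1, and the footnotes to protocol Tables 2 and 3 have questionnaires completed before that visit's dose. That leaves 8 secondary comparisons after baseline: 1 − 0.95^8 = 0.337 if independent. The feasibility condition can only reduce the count. This also stands, and it lowers the figure for a chance secondary finding after baseline.

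The SAP also cites the pilot design and asks for cautious interpretation. That helps less: the caution is tied to the lost within-subject correlation and interaction, not to multiple testing.

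A reader might infer that a false positive is likely or nearly certain. The documents do not support that. It is more likely than not only if most of the 40 comparisons were tested and the correlation among them was not high. A reader might also infer that visits were picked for their p-values. The SAP describes selection by data availability, which is a different matter.

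**Conclusion.** The concern holds in a limited form. The SAP attaches an unadjusted significance rule to all analyses, omits the protocol's exploratory-only limit and its bar on testing five single items, and does not state which tests were done. For the roughly 11 comparisons it marks for testing, the chance of at least one false positive is up to 43%, and about 28-40% under the assumed simulated correlations. The 87% figure applies only if all 40 were tested independently.

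These figures assume no true difference on any outcome, two-sided tests at 0.05, and all 11 (or 40) tests carried out. They cover chance alone. Confounding in a non-randomised comparison and non-random missing data could add spurious findings that no multiplicity adjustment would remove.

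**What to change.** - Replace the significance rule with a statement that all p-values, including the one for compliance, are exploratory, nominal and unadjusted for multiplicity. Reserving the term significant for the primary outcome would not restore the protocol's position, because the protocol makes that analysis exploratory too.
- List every test performed, by outcome and time point.
- Lead with between-group estimates and 95% confidence intervals.
- Keep GF7, CS10, CS11, CS12 and CS13 descriptive, without p-values, as the protocol states. If any were tested, record that as a deviation.
- State that an isolated p<.05 at one visit will not be used to support a larger trial.

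The change is mainly to wording, plus the interval estimates where they have not yet been produced. The downside is that no secondary result, and on the protocol's own terms no primary result, can be called statistically significant. Collapsing the visits into one overall comparison for CCSQ and FACT-BRM would cut the number of tests, but it would need a named method that copes with the non-random missing data, so it is not part of this fix.
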